6.2.4 Overall Survival

Overall survival (OS) is defined as the duration of time from start of treatment to time of death, up to three years from the start of study treatment.

6.2.5 Time to first cytotoxic chemotherapy

Time to first cytotoxic chemotherapy (TTFCC) is defined as the time from start of study treatment to time of first dose of antineioplastic cytotoxic chemotherapy that is administered to treat lymphoma. This does not include corticosteroids, antivirals, or chemotherapeutic agents used for either non-neoplastic diseases or other malignant processes (not lymphoma).

7.0 ADVERSE EVENTS

7.1 Adverse Event Monitoring

Adverse event data collection and reporting, which are required as part of every clinical trial, are done to ensure the safety of subjects enrolled in the studies as well as those who will enroll in future studies using similar agents. Adverse events are reported in a routine manner at scheduled times during a trial. All adverse events will be reported on the appropriate eCRF (as outlined in the guidelines in NOTIS). Additionally, certain adverse events must be reported in an expedited manner to allow for optimal monitoring of patient safety and care.

All patients experiencing an adverse event, regardless of its relationship to study drug, will be monitored until:

- 7.1.1 the adverse event resolves or the symptoms or signs that constitute the adverse event return to baseline;
- 7.1.2 any abnormal laboratory values have returned to baseline;
- 7.1.3 there is a satisfactory explanation other than the study drug for the changes observed; or
- 7.1.4 death.

7.2 Definitions

7.2.1 Definition of Adverse Event

An adverse event (AE) is any untoward medical occurrence in a patient receiving study treatment and which does not necessarily have a causal relationship with this treatment. An AE can therefore be any unfavorable and unintended sign (including an abnormal laboratory finding), symptom, or disease temporally associated with the use of an experimental intervention, whether or not related to the intervention.

7.2.2 Severity of Adverse Events

All non-hematologic adverse events will be graded according to the NCI Common Terminology Criteria for Adverse Events (CTCAE) version 4.03. The CTCAE v4.03 is available at <http://ctep.cancer.gov/reporting/ctc.html>.

If no CTCAE grading is available, the severity of an AE is graded as follows:

- 7.2.2.1 Mild (grade 1): the event causes discomfort without disruption of normal daily activities.
- 7.2.2.2 Moderate (grade 2): the event causes discomfort that affects normal daily activities.
- 7.2.2.3 Severe (grade 3): the event makes the patient unable to perform normal daily activities or significantly affects his/her clinical status.
- 7.2.2.4 Life-threatening (grade 4): the patient was at risk of death at the time of the event.
- 7.2.2.5 Fatal (grade 5): the event caused death.

7.2.3 Serious Adverse Events

All SAEs, regardless of attribution, occurring during the study or within 30 days of the last administration of study drug must be reported to the PI upon discovery or occurrence. Additional expedited or routine reporting may be required, depending on the nature of the SAE (as outlined in 7.4.1 below). A “serious” adverse event is defined in regulatory terminology as any untoward medical occurrence that:

- 7.2.3.1 Results in death.
If death results from (progression of) the disease, the disease should be reported as event (SAE) itself.
- 7.2.3.2 Is life-threatening.
(the patient was at risk of death at the time of the event; it does not refer to an event that hypothetically might have caused death if it were more severe).
- 7.2.3.3 Requires in-patient hospitalization or prolongation of existing hospitalization for ≥ 24 hours.
- 7.2.3.4 Results in persistent or significant disability or incapacity.
- 7.2.3.5 Is a congenital anomaly/birth defect
- 7.2.3.6 Is an important medical event
Any event that does not meet the above criteria, but that in the judgment of the investigator jeopardizes the patient, may be considered for reporting as a serious adverse event. The event may require medical or surgical intervention to prevent one of the outcomes listed in the definition of “Serious Adverse Event”.
For example: allergic bronchospasm requiring intensive treatment in an emergency room or at home; convulsions that may not result in hospitalization; development of drug abuse or drug dependency.

7.2.4 Unanticipated Problems Involving Risks to Subjects or Others (UPIRSOs)

A UPIRSO includes events that are unanticipated in terms of nature, severity, or frequency, place the research subject or others at a different or greater risk of harm, and are deemed to be related or possibly related to participation in the study.

7.3 Steps to Determine If an Adverse Event Requires Expedited Reporting

- 7.3.1 Step 1: Identify the type of adverse event using the NCI CTCAE v 4.03.
- 7.3.2 Step 2: Grade the adverse event using the NCI CTCAE v 4.03.
- 7.3.3 Step 3: Determine whether the adverse event is related to the protocol therapy. Attribution categories are as follows:
 - 7.3.3.1 Definite – The AE is *clearly related* to the study treatment.
 - 7.3.3.2 Probable – The AE is *likely related* to the study treatment.
 - 7.3.3.3 Possible – The AE *may be related* to the study treatment.
 - 7.3.3.4 Unrelated – The AE is *clearly NOT related* to the study treatment.

Note: This includes all events that occur within 30 days of the last dose of protocol treatment. Any event that occurs more than 30 days after the last dose of treatment and is attributed (possibly, probably, or definitely) to the agent(s) must also be reported accordingly.
- 7.3.4 Step 4: Determine the prior experience of the adverse event. Expected events are those that have been previously identified as resulting from administration of the agent. An adverse event is considered unexpected, for expedited reporting purposes only, when either the type of event or the severity of the event is not listed in:
 - 7.3.4.1 the current known adverse events listed in the Agent Information Section of this protocol;
 - 7.3.4.2 the drug package insert;
 - 7.3.4.3 the current Investigator's Brochure

7.4 Reporting Requirements for Adverse Events

7.4.1 Expedited Reporting of SAEs

7.4.1.1 Reporting to the QAM/DMC:

All SAEs must be reported to the assigned QAM within 24 hours of becoming aware of the event. Completion of the NU CRO SAE Form is required. The completed form should assess whether or not the event qualifies as a UPIRSO. The report should also include:

- Protocol description and number
- Patient's Identification Number
- Description of event, severity, treatment, and outcome if known
- Supportive laboratory results and diagnostics
- Hospital Discharge Summary (if available)

All SAEs will be reported to, and reviewed by, the DMC at their next meeting. Reporting to the NU IRB

Any death of an NU subject that is unanticipated in nature and at least possibly related to study participation will be promptly reported to the Northwestern University IRB within 24 hours of notification.

The following SAEs will be reported to the NU IRB within 10 working days of notification:

- Death of a non-NU subject that is unanticipated in nature and at least possibly related to study participation.
- Other UPIRSOs

The following SAEs will be reported to the NU IRB at the time of continuing review:

- All deaths of NU subjects that were not previously reported
- All deaths of non-NU subjects that are deemed to be unanticipated in nature and unrelated to participation
- All other SAEs not previously reported to the NU IRB as UPIRSOs

In addition, participating sites should follow local guidelines for reporting of SAEs to their IRB as required.

7.4.1.2 Reporting to the FDA:

The QAM will notify FDA will be notified within 7 calendar days of any SAE that is associated with study treatment, is unexpected, and is fatal or life-threatening. In these instances, an FDA MedWatch Form will be completed.

7.4.1.3 Reporting to Seattle Genetics:

Any SAE that occurs in a study subject must be reported to Seattle Genetics Drug Safety within 24 hours of first awareness of the event. Notification should be via fax to either [contact] or [contact]. The NU CRO SAE Form is an acceptable method of reporting. The Principal Investigator will assist Seattle Genetics in investigating any SAE and will provide any follow-up information reasonably requested by Seattle Genetics.

7.4.2 Routine Reporting

All other adverse events, such as those that are expected, or are unlikely or definitely not related to the study participation, are to be reported on a regular basis to the assigned QAM for the study in accordance with the Robert H. Lurie Comprehensive Cancer Center's Data Safety Monitoring Plan (DSMP). These will be reviewed by the DMC on an on-going basis. The QAM will notify the FDA within 15 calendar days of any SAE that is associated with the study treatment, unexpected, and serious but not fatal or life-threatening. This includes any previous SAEs that were not initially deemed reportable, but are later determined to meet the criteria for reporting (i.e. by the DMC). A summary of all these events will be reported annually to the NU IRB as part of the continuing review process.

7.5 Stopping Rules

As noted in Section 5.0, the study will be terminated in the event that $\geq 2/3$ patients experience toxicity in cohort -1 (1.2 mg/kg brentuximab vedotin) during Phase I. Likewise, the study will be stopped after the first stage of Phase II if, among the first 15 patients treated, four or fewer patients have a CR or PR, as this will be considered evidence of inadequate efficacy. In addition, the Data Safety Monitoring Committee will monitor the study in accordance with the DSMP and may suspend or close the study to accrual at any point if required, as outlined in the DSMP.

8.0 DRUG INFORMATION**8.1 Brentixumab vedotin**8.1.1 **Other names for the drug(s):** ADCETRIS®**8.1.2 Classification – type of agent**

Antibody-drug conjugate; the antibody is a chimeric IgG1 directed against CD30 and the small molecule, MMAE, is a microtubule disrupting agent.

8.1.3 **Mode of action** The ADC binds to CD30-expressing cells, followed by internalization of the ADC-CD30 complex, and the release of MMAE via proteolytic cleavage. Binding of MMAE to tubulin disrupts the microtubule network within the cell, subsequently inducing cell cycle arrest and apoptotic death of the cells.

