Diagnosis and Main Inclusion Criteria	Adult patients with non-Hodgkin's lymphoma (NHL) related to an immunosuppressed state
Study Product(s), Dose, Route, Regimen	Brentuximab vedotin 1.2 mg/kg IV once weekly for 3 weeks, then 1.8 mg/kg IV once every 3 weeks Rituximab 375 mg/m ² IV once weekly x 4, then once every 6 weeks
Duration of administration	1 year

Statistical Methodology	
Our null hypothesis is that the combination of rituximab and brentuximab vedotin will yield no difference in the ORR as compared to that observed with historical treatments. The historical ORR for both PTLD and EBV-related lymphoma of the elderly, when treated with rituximab (with or without chemotherapy) is estimated at approximately 50% [1, 2]. Therefore, the optimal two-stage design to test the null hypothesis that $P = 0.50$ versus the alternative that $P \geq 0.70$ (the hypothesized ORR to rituximab plus brentuximab vedotin) has an expected sample size of 24. Under these conditions, if the combination is actually not significantly more efficacious, there is a < 0.05 probability (also known as the alpha value) of concluding that it is. If the combination is actually significantly more efficacious, there is a < 0.20 probability (also known as the beta value) of concluding that it is not. Early futility may be declared, such that if 8 or fewer responses are observed among the first 15 patients enrolled, the trial will be stopped and considered no more efficacious than therapy with rituximab alone.

--------------------------------	---

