2.3 Primary Endpoints

- 2.3.1 The primary endpoint for phase I, dose-limiting toxicity (DLT) will be defined as the occurrence of toxicity as detailed in section 4.2 (using CTCAE v 4.03), experienced during the first 3 weeks of study treatment. The MTD, which constitutes the RP2D, will be defined as described in Section 11 (Study Design).
- 2.3.2 The primary endpoint for phase II, response after induction or induction/consolidation, will be defined as the detection of SD, PR, or CR by CT or PET/CT, and/or resolution of marrow-only involvement. CR and PR will each be assessed according to the Revised Response Criteria for Malignant Lymphoma. Assessments will be performed after induction and/or consolidation treatment (if applicable).

2.4 Secondary Endpoints:

- 2.4.1 Adverse events will be defined as those included in CTCAE v 4.03. The occurrence and severity of each will be recorded.
- 2.4.2 PFS will be defined as the time elapsed between treatment initiation and tumor progression or death from any cause (whichever occurs first), with censoring of patients who are lost to follow-up. OS will be defined as freedom from death by any cause.
- 2.4.3 Best response will be assessed by CT or PET/CT according to the Revised Response Criteria for Malignant Lymphoma after induction and/or consolidation (if applicable) and every 12 weeks during maintenance treatment.
- 2.4.4 EBV activation and proliferation will be measured by viral loads as measured at time of enrollment and monthly thereafter in all enrolled patients, until completion of study therapy.
- 2.4.5 Time to initiation of cytotoxic chemotherapy will be defined as the time elapsed between treatment initiation, and time of first non-targeted cytotoxic chemotherapy.
- 2.4.6 Graft rejection will be defined as any of the following: documentation of new or progressive rejection by tissue biopsy of the graft; re-transplantation due to graft rejection; clinical diagnosis of new or progressive graft rejection, since start of treatment on protocol, as given by the patient's transplant physician. Escalation of intensity of immunosuppression will not, by itself, be considered evidence of graft rejection. (Note: patients with clinically active graft rejection will not be excluded from trial enrollment, but will not be considered to have treatment-emergent graft rejection unless progression of rejection is documented.)

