4.0 TREATMENT PLAN

Patients will be treated with combination treatment consisting of brentuximab vedotin and rituximab infusions as detailed below. All patients will receive Induction treatment, and those who achieve response (PR or CR) may have an optional cycle of Consolidation treatment, identical to Induction. Maintenance will then continue for up to one year from the first dose of study treatment.

[figure not shown]

TABLE 1: Dosing Summary

	Induction (1 cycle = 4 weeks)	Consolidation* (1 cycle = 4 weeks)	Maintenance (1 cycle = 3 weeks)
Brentuximab Vedotin dosing	1.2 mg/kg IV over 30 mins Weekly x3	1.2 mg/kg IV over 30 mins Weekly x3	1.8 mg/kg IV over 30 mins Once every 3 weeks
Rituximab dosing	375 mg/m ² IV weekly x4	375 mg/m ² IV weekly x4	375 mg/m ² IV once every 6 weeks

*Optional for patients who achieve PR/CR during induction. See section 4.1.3 for stipulations regarding SD.

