4.9 Patient Replacement

During Phase I, all three patients enrolled at the starting dose level must be observed for one cycle (21 days), at which point the study will be temporarily suspended for toxicity evaluation, before which it may either be reopened for an additional cohort (at either the same dose or a lower dose), or proceed to Phase II (as outlined in sections 4.1.2 and 4.1.3). Any DLT noted at any point after treatment begins (up till the end of the DLT evaluation period) shall count toward the total number of DLT, and patients are not replaced. An exception will be made for those patients who are enrolled but, for whatever reason, never receive treatment; such patients should be replaced. If a patient is withdrawn from the study within 21 days of starting therapy, for whatever reason, but without experiencing a DLT prior to withdrawal, an additional patient may be added to that dose level. Patients missing more than three weeks' worth of doses due to toxicity will not be replaced since these patients will be considered to have experienced a dose limiting toxicity.

During Phase II, any patient who is enrolled but not treated on the study, or who completes fewer than two total cycles of therapy and is withdrawn for any reason except POD or toxicity, shall be replaced.

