Pre-treatment biopsy samples, obtained from pathology archives at NMH, will be identified by a search of corresponding pathological diagnoses in approximately the following numbers:

Non-Hodgkin lymphoma (excluding ALCL) N=100
Diffuse large B-cell lymphoma (DLBCL) N=30
Burkitt lymphoma (BL) N=20
Follicular lymphoma (FL) N=30
Other B-cell lymphoma (mantle cell, marginal zone lymphomas)
N=20
Nasopharyngeal carcinoma N=20
Gastric adenocarcinoma N=20

Each sample will be evaluated by IHC with respect to expression of CD30 and EBV markers (EBER, LMP-1, and EBNA-2). Percentage of positivity will be estimated by an experienced hematopathologist, with values (0-100%) reported both for the malignant lymphoid cells, and for the stromal cells.

This will be a descriptive analysis of the rates of expression of these markers in various disease states, and no formal statistical analysis is planned.

9.2.2 **Objective 2.** Determine whether and to what extent CD30 expression, and expression of EBV markers, predict for response and outcome on this prospective trial:

As described in Objective 1, each sample will be evaluated by IHC with respect to expression of CD30 and EBV markers (EBER, LMP-1, and EBNA-2). Percentage of positivity will be estimated by an experienced hematopathologist, with values (0-100%) reported both for the malignant lymphoid cells, and for the stromal cells.

In univariate and multivariate analyses, these percentages will be correlated with response (CR/PR vs SD/PD), and PFS.

9.2.3 **Objective 3.** Determine whether a multivariate model of outcome in PTLD can be prospectively validated, and whether expression of CD30 and EBV markers can be incorporated into a multi-factorial prognostic model for PTLD:

We will evaluate the model described above [12] in the patients treated as part of this trial. We will additionally incorporate CD30 expression and markers of EBV into a multivariate analysis to determine whether a more precise clinicopathologic model of prediction is possible.

9.2.4 **Objective 4.** Determine whether changes in serum levels of EBV correlate with response and subsequent loss of response to therapy:

Serum EBV levels will be followed as standard of care, and will be evaluated as a dichotomous variable (undetectable vs detectable). Loss of detectable EBV will be correlated with response (CR/PR vs SD/PD), and emergence of detectable EBV will likewise be correlated with loss of response.

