10.1.2 Phase II

Our null hypothesis is that the combination of rituximab and brentuximab vedotin will yield no difference in the rate of ORR as compared to that observed with historical treatments. The historical ORR for both PTLD and EBV-related

lymphoma of the elderly, when treated with rituximab (with or without chemotherapy is estimated at approximately 50% [1, 2]. Therefore, the optimal two-stage design to test the null hypothesis that $P=0.50$ versus the alternative that $P>=0.70$ (the hypothesized ORR to rituximab plus brentuximab vedotin) has an expected sample size of 24. Under these conditions, if the combination is actually not significantly more efficacious, there is a <0.05 probability (also known as the alpha value) of concluding that it is. If the combination is actually significantly more efficacious, there is a <0.20 probability (also known as the beta value) of concluding that it is not. Early futility may be declared, such that if eight or fewer responses are observed among the first 15 patients enrolled, the trial will be stopped and considered no more efficacious than therapy with rituximab alone.

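### Section 7.5 sets the Phase II first-stage futility limit at 4 of 15 responses; section 10.1.2 and the Study Summary set it at 8 of 15, and only 8 of 15 matches the stated design

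*Combined protocol and SAP*

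**What the plan says.** Three places in the current text describe the first-stage efficacy look in Phase II.

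- Section 7.5 (Stopping Rules): the study stops if "among the first 15 patients treated, four or fewer patients have a CR or PR".
- Section 10.1.2 (Phase II): "if eight or fewer responses are observed among the first 15 patients enrolled, the trial will be stopped". The same sentence opens permissively, saying that futility may be declared.
- Study Summary, Statistical Methodology: "if 8 or fewer responses are observed among the first 15 patients enrolled, the trial will be stopped".

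The counted event also varies. Section 7.5 names CR or PR, while section 10.1.2 and the Study Summary say only responses. The Phase II primary endpoint in section 2.3.2 "will be defined as the detection of SD, PR, or CR by CT or PET/CT". Elsewhere response means CR or PR: section 4.0 says "those who achieve response (PR or CR) may have an optional cycle of Consolidation treatment", and section 9.2.2 has marker levels "correlated with response (CR/PR vs SD/PD), and PFS".

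The base differs too: the first 15 *treated* in section 7.5, the first 15 *enrolled* in the other two places.

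**The concern.** One look at 15 patients cannot have two limits. With 5, 6, 7 or 8 responders, section 10.1.2 ends the trial and section 7.5 does not. Section 7.5 is the section headed as the stopping rules, and it is where the monitoring committee's role is described, so it could well be the one consulted.

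At stake is protection against continuing an inactive regimen. Section 10.1.2 treats a result of eight or fewer as no better than rituximab alone; under section 7.5 taken alone, enrolment would go on towards 24. The committee may close the study at any point, but it is handed two conflicting numerical triggers. If SD could also be counted as a response, even the limit of eight would be weaker than it looks.

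**Working it through.** **Inputs.** Section 10.1.2: p0 = 0.50, p1 = 0.70, alpha < 0.05, beta < 0.20, optimal two-stage design, expected sample size 24, first stage of 15. Section 10.2: 24 patients in Phase II, accrual 1.5 per month. Section 3.0: at least 5 accrued per month. Responses are CR or PR unless stated.

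**1. Reproducing the stated design.** An exhaustive exact-binomial search for the two-stage design with the smallest expected N under p0, subject to alpha ≤ 0.05 and power ≥ 0.80, gives: stop at ≤ 8 of 15, otherwise continue to 43 and declare activity at more than 26 responses. Alpha is 0.0499 and power 0.8044. Null expected N = 15 + (1 − 0.6964) × (43 − 15) = 23.50, which rounds to the stated 24.

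**2. Can 4 of 15 be that design?** With the first stage fixed at ≤ 4 of 15, the design meeting both error rates with the smallest null expected N is 23/37 (alpha 0.0494, power 0.8071): 15 + (1 − 0.0592) × (37 − 15) = 35.70. Using 4 of 15 with the 26/43 final rule gives alpha 0.0631 and null expected N 41.3. Neither is the stated design.

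**3. Probability of stopping at 15.** X ~ Binomial(15, p).

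| True ORR | P(X ≤ 8) | P(X ≤ 4) | P(5 ≤ X ≤ 8) |
|---|---|---|---|
| 30% | 0.985 | 0.515 | 0.469 |
| 40% | 0.905 | 0.217 | 0.688 |
| 50% | 0.696 | 0.059 | 0.637 |
| 60% | 0.390 | 0.009 | 0.381 |
| 70% | 0.131 | 0.001 | 0.130 |

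The last column is the probability that the two rules give opposite answers.

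**4. Further patients treated at the null if section 7.5 is used alone.** The average is 0.637 × (9 − patients already enrolled when patient 15 is read), where 9 = 24 − 15.

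- Accrual paused at 15: 0.637 × 9 = 5.7. No Phase II pause is written. Section 4.9 describes one for Phase I only: "at which point the study will be temporarily suspended for toxicity evaluation".
- No pause, 1.5 per month, assuming 1 to 2.5 months to read patient 15: 0.637 × 7.5 = 4.8 down to 0.637 × 5.25 = 3.3.
- No pause, 5 per month: 0.637 × 4 = 2.5 at one month, and 0 by two months.

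**5. Error rates with a maximum of 24.** No final cut-off is printed, so several are shown as alpha / power.

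| Success if more than | With 8 of 15 | With 4 of 15 |
|---|---|---|
| 14 of 24 | 0.132 / 0.802 | 0.154 / 0.847 |
| 15 of 24 | 0.072 / 0.708 | 0.076 / 0.725 |
| 16 of 24 | 0.032 / 0.561 | 0.032 / 0.565 |

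**6. If SD counted as a response.** The plan gives no SD rate. Assuming 10% or 20% on top of a 50% ORR, the counted event has probability 0.60 or 0.70, and stopping under ≤ 8 of 15 falls from 0.696 to 0.390 or 0.131.

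**The case against.** The rules are nested, and both are written as sufficient conditions for stopping. Anyone who follows the whole protocol stops at eight, so the fall from 0.696 to 0.059 requires section 7.5 to be used without the statistics section. That is right and limits the harm to that case, but the text does not say which section prevails.

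The maximum of 43 and the final cut-off of 26 are not printed. If 24 is read as the maximum, null expected N is 15 + 0.3036 × 9 = 17.7 under 8 of 15 and 15 + 0.9408 × 9 = 23.5 under 4 of 15, so the figure 24 alone does not single out eight. This also stands, but it does not rescue 4 of 15: at 24 patients no final cut-off meets both error rates under either limit. The stated optimal design with its stated error rates still points to eight.

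The practical harm is modest: final alpha and power hardly move, and without a pause the average excess at 1.5 patients per month is 3.3 to 4.8. The figure of 5 per month is itself doubtful, because section 3.0 says about 2 potentially eligible patients are seen monthly.

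Finally, the SD clause in section 2.3.2 is a primary-endpoint defect in its own right, and CR or PR is the natural reading of ORR in section 10.1.2. It still matters here, because correcting the limit alone would leave the counted event undefined in two of the three places.

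**Conclusion.** The concern holds. The plan gives two incompatible limits for its only planned interim efficacy decision, and the limit in section 7.5 does not belong to the design the plan says it uses. Applied alone, it cuts stopping from 0.696 to 0.059 at a true ORR of 50%, and from 0.905 to 0.217 at 40%. At 50% the rules conflict with probability 0.637. Up to 9 further patients could be treated after a result that section 10.1.2 says ends the trial, 5.7 on average if accrual pauses at 15 and fewer if it does not.

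The stopping probabilities rest only on the binomial model and the printed limits. The match to 8 of 15 rests on the stated rates, error limits and the word optimal. The accrual results depend on an assumed reading time, the SD results on assumed SD rates, and the results at 24 patients on an assumed final cut-off. This must be fixed.

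**What to change.** - In section 7.5, change four to eight. This is one word.
- In section 7.5, section 10.1.2 and the Study Summary, state that a response for this look is CR or PR. Reconcile section 2.3.2 so that SD does not count toward the ORR being tested. In section 10.1.2 and the Study Summary, replace the mix of permissive and mandatory wording with one form.
- Use one definition of the first 15. *Treated* fits the replacement of never-treated patients in section 4.9. That section also replaces a treated patient who completes fewer than two cycles and "is withdrawn for any reason except POD or toxicity, shall be replaced", so say whether that patient or the replacement counts.
- Do not base the look on the response-evaluable subset of section 6.2.1.1. It keeps early documented progression, but can drop early toxicity withdrawals and deaths without documented progression, and section 4.9 does not replace toxicity withdrawals.
- If the look has already taken place, record in the amendment which limit was applied.

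The cost is short text edits and no new procedures. The section 2.3.2 edit touches the primary endpoint, so it belongs in an IRB-approved amendment.

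Two related matters stay open: the use of 24, an expected sample size, as the Phase II total, and how fully resected patients (section 3.1.3) count among the 15.
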